Appendix I Ceralasertib Guidelines for Potential Interactions with Concomitant Medications

Ceralasertib is an investigational drug for which no data on *in vivo* interactions are currently available. Potential interaction is considered on the basis of preclinical *in vitro* data only.

The lists of CYP and transporter inhibitors/inducers, and CYP and transporter substrates are available in below. They are not exhaustive and the absence of a drug from these lists does not imply that its combination with ceralasertib is safe. If ceralasertib is being administered in combination, potential interactions of the combination partner should also be considered.

Restrictions regarding drugs affection CYP metabolism

There are currently no data confirming that there is a pharmacokinetic (PK) interaction between these agents and ceralasertib; a potential interaction is considered on the basis of preclinical and *in vitro* data only. ceralasertib is predominantly eliminated via CYP3A metabolism, therefore CYP3A inhibitors or inducers may increase or decrease exposure to ceralasertib, respectively. Potent inhibitors or inducers of CYP3A should not be combined with ceralasertib. *In vitro* data also suggest that ceralasertib may be metabolised by CYP2A8 but a lesser extent, therefore caution should be applied with co administration of potent inhibitors or inducers of CYP2C8.

These lists are not intended to be exhaustive, and similar restrictions will apply to other agents that are known to modulate CYP3A activity or CYP2C8. Please contact AstraZeneca with any queries you have on this issue. Please refer to full prescribing information for all drugs prior to co-administration with ceralasertib.

App. Table 5: Drugs known to be inhibitors and inducers of CYP3A

Potent CYP3A inhibitors	Potent CYP3A inducers
boceprevir ceritinib clarithromycin cobicistat (GS-9350) conivaptan danoprevir / RIT elvitegravir / RIT grapefruit juice[2] idelalisib indinavir indinavir /RIT itraconazole ketoconazole LCL161 lopinavir / RIT mibefradil mifepristone nefazodone nelfinavir posaconazole ribociclib ritonavir saquinavir saquinavir / RIT telaprevir telithromycin tipranavir/RIT troleandomycin VIEKIRA PAK2[1] voriconazole	apalutamide avasimibe carbamazepine enzalutamide ivosidenib lumacaftor mitotane phenobarbital phenytoin rifampin rifapentine St John's Wort extract

List created using the University of Washington Drug-Drug Interaction Database Jan 2012.

RIT=Ritonivir. Ritonavir has dual effects of simultaneous CYP3A inhibition and induction, and the net pharmacokinetic outcome during chronic ritonavir therapy is inhibition of CYP3A activity

[1] VIEKIRA PAK = 150/100 mg paritaprevir/ritonavir + 25 mg ombitasvir + 800 mg dasabuvir for 28 days. [2]. Double-strength grapefruit juice. Patients should abstain from eating large amounts of grapefruit and Seville oranges (and other products containing these fruits e.g., grapefruit juice or marmalade) during the study (e.g., no more than a small glass of grapefruit juice (120 mL) or half a grapefruit or 1-2 teaspoons (15 g) of Seville orange marmalade daily

App. Table 6: Drugs known to be inhibitors and inducers of CYP2C8

Potent CYP2C8 inhibitors	Potent CYP2C8 inducers
gemfibrozil clopidogrel	None identified

List created using the University of Washington Drug-Drug Interaction Database Jan 2020.

Drugs known to be inhibitors or inducers of Pgp and/or BCRP, undertake appropriate monitoring if coadministration is necessary

Ceralasertib is a substrate of Pgp and BCRP. Co-administration of Pgp inhibitors/inducers or BCRP inhibitors/inducers may affect exposure to ceralasertib therefore it is recommended that these are not co-administered with ceralasertib.

These lists are not intended to be exhaustive, and similar restrictions will apply to other agents that are known to modulate Pgp activity or BCRP activity. Please contact AstraZeneca with any queries you have on this issue. Please refer to full prescribing information for all drugs prior to co-administration with ceralasertib.

App. Table 7: Drugs known to be inhibitors or inducers of P-gp

Drugs Known to be Inhibitors of Pgp ^a	Drugs Known to be Inducers of Pgp ^b
Amiodarone azithromycin captopril carvedilol clarithromycin conivaptan cremophor curcumin diltiazem dronedarone elacridar erythromycin felodipine fluvoxamine ginkgo indinavir itraconazole ketoconazole lapatinib lopinavir and ritonavir mibefradil milk thistle mirabegron nelfinavir nifedipine nitrendipine paroxetine quercetin quinidine ranolazine rifampin ritonavir saquinavir/ritonavir schisandra chinensis extract St Johns Wort talinolol telaprevir telmisartan ticagrelor tipranavir/ritonavir tolvaptan valsopodar (PSC 833) verapamil	avasimibe carbamazepine efavirenz genistein phenytoin rifampin St Johns Wort

a. Inhibitors listed for P-gp are those that showed >25% increase in exposure to a P-gp substrate (e.g. digoxin).

b. Inducers listed for P-gp are those that showed >20 % decrease in exposure to a P-gp substrate (e.g. digoxin)

App. Table 8: Drugs known to be inhibitors or inducers of BCRP

Drugs Known to be Inhibitors of BCRP	Drugs Known to be inducers of BCRP
Afatinib Aripiprazole Curcumin Cyclosporine Elacridar Erlotinib Fluvastatin Fumitremorgin Gefitinib Ivermectin Lapatinib Nilotinib Novobiocin Pantoprazole Pitavastatin Ponatinib Quercetin Quizartinib Rabeprazole Regorafenib Rilpivirine Sulfasalazine Sunitinib Tacrolimus Teriflunomide Trametinib Trifluoperazine Vismodegib eltrombopag Atazanavir Lopinavir Ritonavir Tipranavir Omeprazole Estrone 17b-estradiol Imatinib mesylate	Please check individual drugs on a case by case basis

List created using <http://dmd.aspetjournals.org/content/dmd/43/4/490.full.pdf>

Note: Although BCRP is involved in a number of clinically relevant DDIs, none of the cited inhibitors above is truly specific for this transporter

Drugs known to be substrates of CYP3A4 and/or CYP2B6, undertake appropriate monitoring if coadministration is necessary

Ceralasertib is a potential inducer of CYP3A4 and CYP2B6. Therefore caution should be applied with co administration of drugs that are either completely metabolised by CYP3A4 and/or CYP2B6, or that are substrates of CYP3A4 and/or CYP2B6 and also have a narrow therapeutic index. Investigators should be aware that the exposure of other drugs metabolised by CYP3A4 and/or CYP2B6 may be reduced.

App. Table 9: Drugs known to be metabolised by CYP3A4 and have a narrow therapeutic index

Alfentanil Cyclosporine Dihydroergotamine Ergotamine Fentanyl Pimozide Quinidine Sirolimus Tacrolimus Astemizole Cisapride Terfenadine

App. Table 10: Drugs known to be metabolised by CYP2B6 and have a narrow therapeutic index

Cyclophosphamide Ifosfamide Efavirenz Bupropion Propofol Thiotepa Sorafenib alfentanil ketamine methadone methoxetamine nevirapine propofol selegiline sertraline sorafenib tamoxifen valproic acid
--

From Flockhart DA (2007). "Drug Interactions: Cytochrome P450 Drug Interaction Table". Indiana University School of Medicine

Drugs known to be substrates of OATP1B1 and BCRP, undertake appropriate monitoring if coadministration is necessary

Ceralasertib is also an inhibitor of OATP1B1 and BCRP. Caution should be applied with coadministration of substrates of OATP1B1 and/or BCRP as ceralasertib may increase their exposure.

$C_{\min ss}$	Minimum concentration at steady state
CR	Complete response
CRO	Contract Research Organisation
CSR	Clinical Study Report
CT	Computed tomography
CTCAE	Common Terminology Criteria for Adverse Event
CV	Coefficient of variation
DAE	Discontinuation of Investigational Product due to Adverse Events
DNA	Deoxyribonucleic acid
DoR	Duration of response
ECG	Electrocardiogram
ECOG PS	Eastern Cooperative Oncology Group performance status: a performance status using scales and criteria to assess how a patient's disease is progressing

Abbreviation or special term	Explanation
eCRF	Electronic case report form
EDoR	Expected duration of response
CCI	CCI
FAS	Full analysis set
HR	Hazard ratio
HRR	Homologous Recombination Repair
HRR _m	Homologous Recombination Repair gene mutation
ID	Identification
IPD	Important protocol deviation
ISRC	Independent Safety Review Committee
KM	Kaplan-Meier
LLoQ	Lower limit of quantification
MedDRA	Medical Dictionary for Regulatory Activities
MRI	Magnetic resonance imaging
CCI	
NC	Not calculable
NE	Not evaluable
NED	No evidence of disease
NPD	Non-progressive disease
NQ	Not quantifiable
NTL	Non-target lesion
MDS	Myelodysplastic syndrome
OAE	Other significant adverse event
Od	Once daily
ORR	Objective response rate
OS	Overall survival
PD	Progressive disease
PFS	Progression free survival
PK	Pharmacokinetics
PR	Partial response
CCI	
CCI	CCI

Abbreviation or special term	Explanation
RDI	Relative dose intensity
RECIST	Response Evaluation Criteria In Solid Tumours
SAE	Serious Adverse Event
SAF	Safety analysis set
SAP	Statistical Analysis Plan
SD	Stable disease
SD	Standard deviation
SI	International System of Units (Système international d'unités)
TL	Target lesion
TNBC	Triple Negative Breast Cancer
tsm	Tumour size measurement
ULN	Upper limit of normal
ULoQ	Upper limit of quantification
URC	Unblinded review committee

Statistical Analysis Plan
Drug Substances Olaparib / AZD6738 / AZD1775
Study Code D5336C00001
Version 2.0
Date 14 Jun 2019

STATISTICAL ANALYSIS PLAN AMENDMENT HISTORY

Date	Brief description of change
5Dec2017	Initial Version
Effective date of last signature	Updated for consistency with Protocol Amendment 6.0 (29 Apr 2019) in which urgent safety issue resulted in AZD1775+olaparib arm being closed to recruitment

1. STUDY DETAILS

1.1 Study objectives

Study objectives are defined for the following patient populations (strata A, B, C are explained in Section 1.2.1, *BRCAm* stands for BReast CAncer susceptible gene mutation, *HRRm* stands for Homologous Recombination Repair gene mutation):

- “*BRCAm*” = patients from stratum A
- “*HRRm*” = patients from stratum A and patients from stratum B
- “Non *BRCAm* *HRRm*” = patients from stratum B
- “All” = patients from any stratum
- “Non *HRRm*” = patients from stratum C

1.1.1 Primary objective

Patient Population	Primary Objective	Outcome Measure

 • BRCAm • Non BRCAm HRRm • Non HRRm 	To assess the efficacy of the combination of AZD6738+Olaparib and the combination of AZD1775+Olaparib compared with Olaparib monotherapy by assessment of progression-free survival (PFS)	
PFS using Blinded Independent Central Review (BICR) according to Response Evaluation Criteria In Solid Tumours (RECIST) 1.1
 
Sensitivity analysis of PFS using Investigator assessments according to RECIST 1.1

1.1.2 Secondary objectives

Patient Population	Secondary Objectives	Outcome Measures

 • HRRm • All 	To assess the efficacy of the combination of AZD6738+Olaparib and the combination of AZD1775+Olaparib compared with Olaparib monotherapy by assessment of PFS	
PFS using BICR according to RECIST 1.1
 
Sensitivity analysis of PFS using Investigator assessments according to RECIST 1.1

 • BRCAm • HRRm • Non BRCAm HRRm • All • Non HRRm 	To assess the efficacy of the combination of AZD6738+Olaparib and the combination of AZD1775+Olaparib compared with Olaparib monotherapy in terms of objective response rate (ORR)	
ORR using BICR according to RECIST 1.1
 
Sensitivity analysis of ORR using Investigator assessments according to RECIST 1.1

Patient Population	Secondary Objectives	Outcome Measures

 • BRCAm • Non BRCAm HRRm • Non HRRm 	To assess the efficacy of the combination of AZD6738+Olaparib and the combination of AZD1775+Olaparib compared with Olaparib monotherapy in terms of duration of response (DoR) and tumour change	DoR and tumour change using BICR according to RECIST 1.1 Sensitivity analysis of DoR, and tumour change using Investigator assessments according to RECIST 1.1

 • BRCAm • HRRm • Non BRCAm HRRm • All • Non HRRm 	To assess the efficacy of the combination of AZD6738+Olaparib and the combination of AZD1775+Olaparib compared with Olaparib monotherapy in terms of overall survival (OS)	Time to death for any cause

 • BRCAm • HRRm • Non BRCAm HRRm • All • Non HRRm 	To compare the efficacy of the combination of AZD6738+Olaparib with the combination of AZD1775+Olaparib in terms of PFS and ORR	PFS and ORR using BICR according to RECIST 1.1 Sensitivity analysis of PFS and objective response using Investigator assessments according to RECIST 1.1

 • BRCAm • Non BRCAm HRRm • Non HRRm 	To compare the efficacy of the combination of AZD6738+Olaparib with the combination of AZD1775+Olaparib in terms of DoR and tumour change	DoR and tumour change using BICR according to RECIST 1.1 Sensitivity analysis of DoR and tumour change using Investigator assessments according to RECIST 1.1

 • BRCAm • HRRm • Non BRCAm HRRm • All • Non HRRm 	To compare the efficacy of the combination of AZD6738+Olaparib with the combination of AZD1775+Olaparib in terms of OS	Time to death for any cause

 • All 	To explore the frequency of and describe the nature of tumour HRR (including BRCA) mutation(s) in tumour samples and to compare this with germline HRR (including BRCA) mutation status	Mutation status of cc1 genes

 • All 	To assess exposure to Olaparib, AZD6738 and AZD1775 in all patients	Minimum concentration at steady state ($C_{\min ss}$)

1.1.3 Safety objectives

Patient Population	Safety Objective	Outcome Measure

 All 	To assess the safety and tolerability of the combination of AZD6738+Olaparib and the combination of AZD1775+Olaparib compared with Olaparib monotherapy	
 Adverse Events (AEs), severity graded by Common Terminology Criteria for Adverse Event (CTCAE) v4 laboratory tests (clinical chemistry, haematology and urinalysis) vital signs: pulse and blood pressure electrocardiogram (ECG) data Eastern Cooperative Oncology Group performance status (ECOG PS)

1.1.4 Exploratory objectives

Not all data generated as part of exploratory objectives will be included in the Clinical Study Report (CSR); respective analyses will be reported separately and are not covered by this Statistical Analysis Plan (SAP).

Patient Population	Exploratory Objectives	Outcome Measure

 BRCAm HRRm Non BRCAm HRRm All Non HRRm 	CCI [REDACTED] [REDACTED] [REDACTED]	CCI [REDACTED] [REDACTED] [REDACTED] - [REDACTED] [REDACTED] [REDACTED]

1.2 Study design

This is a prospective, open label, randomised, multi-centre Phase 2 study that will assess the efficacy and safety of Olaparib monotherapy versus Olaparib in combination with an inhibitor of ATR (AZD6738) and Olaparib monotherapy versus Olaparib in combination with an inhibitor of WEE1 (AZD1775) in second or third line setting in patients with Triple Negative Breast Cancer (TNBC) prospectively stratified by presence/absence of qualifying tumour mutation in genes involved in the HRR pathway.

1.2.1 Stratification of patient population

The study patient population will be stratified as described below:

- stratum A: patients with tumour mutations in *BRCA1* or *BRCA2* (*BRCAm*)
- stratum B: patients with tumour mutations in any of the following **CCI** genes involved in the Homologous Recombination Repair (HRR) pathway (**CCI** [REDACTED],

CCI

and no mutation in *BRCA1* and no mutation in *BRCA2*

- stratum C: patients that have no detected tumour mutations in any of the CCI HRR genes mentioned above.

Within each stratum A, B and C, there will be further stratification by whether the patient received prior platinum-based therapy (yes/no) as defined in the study protocol

1.2.2 Treatment arms

The 3 treatment arms are:

- Treatment Arm 1: 300 mg twice daily (bd) Olaparib continuous (28-day cycle)
- Treatment Arm 2: 160 mg once daily (od) AZD6738 Days 1-7 + 300 mg bd Olaparib continuous (28-day cycle)
- Treatment Arm 3: 175 mg bd AZD1775 Days 1-3 and 8-10 + 200 mg bd Olaparib continuous (21-day cycle) (Randomization to treatment arm 3 closed April 2019. Existing patients will continue receiving Olaparib monotherapy or discontinue all study treatment.)

Due to the different schedules of administration of each of the treatment options as well as their different toxicity profiles, the study cannot be blinded for patients and site personnel. Given the open label design of the study, efforts will be made to ensure robustness of the primary endpoint assessment (including the BICR) and to avoid any unnecessary unblinding of the operational study team. Details are described in a separate study-specific Blinding Maintenance Plan.

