8.5 Methods for statistical analyses

All efficacy analyses will be performed on the FAS. Results of statistical analyses will be presented using 90% CIs and 2-sided p-values.

Pairwise comparisons between the ceralasertib + olaparib vs. olaparib monotherapy, AZD1775+olaparib vs. olaparib monotherapy and ceralasertib + olaparib vs. AZD1775+olaparib will be generated for each endpoint.

Following the decision of the ISRC to close recruitment to the AZD1775 + olaparib arm, the study will only be sized to detect a difference for the ceralasertib + olaparib vs olaparib monotherapy comparison, although all the available data across all 3 arms, where possible, will be used in the statistical models.

As the starting dose of the AZD1775+Olaparib arm was refined during the study, for any comparisons including the AZD1775+olaparib arm, all AZD1775+olaparib patients regardless of their starting dose will be included in the analyses. Additional sensitivity analyses may be carried out which only including those patients AZD1775+Olaparib patients who start treatment on the revised starting dose.

The assignment of a patient to each of the populations will be based on the values entered into IVRS at randomisation, even if it is subsequently discovered that these values were incorrect or not confirmed by the central FMI assay. If there are any patients who were wrongly assigned, a sensitivity analysis may be carried out with patients in the population they should have been assigned to.

The stratification in the statistical modelling will be based on the values entered into IVRS at randomisation, even if it is subsequently discovered that these values were incorrect. If there are any patients who were mis-stratified, a sensitivity analysis will be carried out using the (correct) baseline data collected in the eCRF.

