2.1.2 Safety analysis set

The safety analysis set (SAF) will include all patients who received at least one dose of study treatment (regardless of whether that was the randomised therapy intended or indeed whether, in rare cases, they received therapy without being randomised), according to the study treatment they actually received, defined as below:

- if a patient received at least one dose of Olaparib, no dose of AZD6738 and no dose of AZD1775, then the patient will be counted for treatment arm 1 (Olaparib alone) in the SAF
- if a patient received at least one dose of AZD6738 and no dose of AZD1775, then the patient will be counted for treatment arm 2 (AZD6738 + Olaparib) in the SAF
- if a patient received at least one dose of AZD1775 and no dose of AZD6738, then the patient will be counted for treatment arm 3 (AZD1775 + Olaparib) in the SAF
- if a patient received at least one dose of AZD1775 and at least one dose of AZD6738, then it will be decided at the Blinded Data Review Meeting to which treatment arm the patient will be assigned for the safety analysis.

All safety data and drug exposure data will be summarised and analysed using the SAF.

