4.2.5 PFS sensitivity analyses for the 3 primary patient populations

The following PFS sensitivity analyses will be considered:

- ascertainment bias: refers to possible bias introduced by disagreement between site investigator and BICR assessments and subsequent informative censoring in PFS analyses of the BICR data.
- evaluation-time bias: refers to the possibility that the PFS effect is partly an artefact of one arm being assessed more frequently
- attrition bias: refers to the possibility that the rate and nature of censoring has resulted in bias

Ascertainment bias

The primary analyses of PFS will be repeated using investigator assessed RECIST data. The p-value from the stratified log-rank test, and the HR and 90% CI from the stratified proportional hazards model will be presented for each pairwise comparison.

Disagreements between investigator and central reviews of RECIST progression will be presented for each treatment group. The summary will include the early discrepancy rate which is the frequency of central review declared progressions before the investigator review as a proportion of all central review progressions and the late discrepancy rate which is the frequency of central review declared progressions after the investigator review as a proportion of all discrepancies.

If there is an important discrepancy between the primary analysis using BICR RECIST-based data and this sensitivity analysis using the site investigator RECIST-based data then the proportion of patients with site but no central confirmation of progression will be summarised; such patients have the potential to induce bias in the BICR RECIST-based PFS analysis due to informative censoring. An approach of imputing an event at the next visit in the central review analysis may help inform the most likely HR value (Fleischer et al 2011), but only if an important discrepancy exists between site investigator and BICR data exists. Note: it is the blinded study team's responsibility to determine whether there is an important discrepancy upon blinded review of the data, and whether such further analyses are required.

Evaluation-time bias

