4.2.8.8 Analysis of exposure data

Total and actual exposure (expressed in days) of exposure for all 3 study treatments will be summarised by treatment arm.

A frequency table for number of treatment cycles for all 3 study treatments will be produced by treatment arm.

Analysis of dose interruptions and reductions

Descriptive summaries by treatment arm and study treatment will be produced for

- number and duration of dose of dose interruptions
- number, type and duration of dose of dose reductions.

Analysis of the duration of the safety follow-up

A frequency table for the duration of the safety follow-up will be produced by treatment arm.

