4.2.10 Analysis of safety and tolerability data

4.2.10.1 Analysis of adverse events

Summary tables mentioned below will include all treatment emergent AEs (as defined in Section 3.5.4). Any events in this period that occur after a patient has received further therapy for cancer (following discontinuation of study treatment) will be flagged in AE data listings.

Summaries by treatment arm, displaying MedDRA System Organ Class (SOC) and Preferred Term (PT) of treatment emergent AEs will include number (%) of patients who have:

- At least one AE (for All patient population and each of the 3 primary patient populations)
- At least one AE with CTCAE grade ≥ 3 (for All patient population and each of the 3 primary patient populations)
- At least one AE by maximum CTCAE grade
- At least one AE causally related to study medication (separately for investigational product in the combination treatment arms)
- At least one AE with CTCAE grade ≥ 3 causally related to study medication (separately for investigational product in the combination treatment arms)
- At least one AE leading to discontinuation of study treatment (for All patient population and each of the 3 primary patient populations)
- At least one OAE
- At least one SAE (for All patient population and each of the 3 primary patient populations)
- At least one SAE causally related to study medication (separately for investigational product in the combination treatment arms)

An overall summary of the number and percentage of patients in each category bulleted above will be presented, as well as an overall summary of the number of events in each category. In addition, a truncated AE table of most common AEs, showing all PTs that occur in at least 5% of patients overall will be summarised by preferred term, by decreasing frequency. This cut-off may be modified after review of the data.

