6. CHANGES OF ANALYSIS FROM PROTOCOL

Not applicable.

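### SAP 1.2.2 gives only the superseded 175 mg bd AZD1775 dose for Arm 3, SAP 3.5.3 leaves the intended dose for relative dose intensity undefined, and no planned table shows tolerability at the revised 150 mg bd dose

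*SAP*

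**What the plan says.** SAP section 1.2.2 (version 2.0, 14 June 2019) defines Arm 3 as "175 mg bd AZD1775 Days 1-3 and 8-10 + 200 mg bd Olaparib continuous" on a 21-day cycle. The entry also records the April 2019 closure, so it was edited after the dose had changed. The SAP's amendment history says this version was brought into line with protocol version 6.0.

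The protocol's version history places the cut to 150 mg bd in version 5.0 (3 July 2018). The current text agrees: the synopsis and sections 1.4 and 7.2 give 150 mg bd, and section 1.2.2 explains that safety findings in this arm led to the change. On analysis, protocol section 8.5 states that for comparisons involving this arm "all AZD1775+olaparib patients regardless of their starting dose will be included in the analyses". It adds: "Additional sensitivity analyses may be carried out which only including those patients AZD1775+Olaparib patients who start treatment on the revised starting dose".

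SAP section 2.1.2 assigns patients to the safety set by drug taken: a patient who "received at least one dose of AZD1775 and no dose of AZD6738, then the patient will be counted for treatment arm 3". Section 4.1.2 gives every output three arms. Section 4.2.10.1 plans "Summaries by treatment arm, displaying MedDRA System Organ Class (SOC) and Preferred Term (PT) of treatment emergent AEs", and for interruptions and reductions section 4.2.8.8 states "Descriptive summaries by treatment arm and study treatment will be produced for" their number and duration. Section 3.5.3 defines RDI as 100% × d/D, where d is the cumulative dose delivered and D the cumulative dose intended had nothing been modified. It does not say from which starting dose D is built.

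**The concern.** A SAP is the specification that programmers work from. Here the only AZD1775 dose it offers is one withdrawn about 11 months earlier, and the one derived variable that needs an intended dose does not say where to find it. The natural place to look is section 1.2.2, and that would give a wrong RDI for every patient who started at 150 mg bd.

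The second matter is reporting. Safety and tolerability of AZD1775+olaparib is an objective in SAP section 1.1.3. The dose was lowered for safety, yet the planned tables for grade 3 or higher AEs, discontinuations, dose reductions and dose intensity carry a single AZD1775+Olaparib column. A reader of the study report could not see how the revised dose was tolerated, or how many patients started on it.

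**Working it through.** **The plan's own figure.** The plan gives no RDI or AE figure to reproduce. The nearest design figure is 68 PFS events for 80% power at HR 0.55 and two-sided 10%. By Schoenfeld's formula with 1:1 allocation, √(68/4) × |ln 0.55| − 1.645 = 4.123 × 0.598 − 1.645 = 0.82, a power of 79.4%. The figure reproduces, and no AZD1775 dose enters it.

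**Inputs for the dose check.**
- Original starting dose: 175 mg bd (SAP 1.2.2; named as the earlier dose in protocol 1.2.2).
- Revised starting dose: 150 mg bd (protocol 1.4).
- Dosing days per 21-day cycle: Days 1–3 and 8–10, so 6 days with two doses each.

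**Intended AZD1775 per cycle.**
- 175 × 2 × 6 = 2100 mg
- 150 × 2 × 6 = 1800 mg

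**RDI for a patient who takes every planned dose**, under three readings of D:

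| D taken from | 175 mg starter | 150 mg starter |
|---|---|---|
| SAP 1.2.2 (175 mg for all) | 2100/2100 = 100% | 1800/2100 = 85.7% |
| Current protocol (150 mg for all) | 2100/1800 = 116.7% | 1800/1800 = 100% |
| Patient's own starting dose | 100% | 100% |

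Only the third reading measures adherence to plan in both groups.

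**Effect on the arm mean.** The number of patients per starting dose is not given. Let f be the fraction who started at 175 mg. With D fixed at 175 mg, the highest attainable mean RDI is f × 100% + (1 − f) × 85.7%. Over an assumed range for f:
- f = 0.1: 87.1%
- f = 0.5: 92.9%
- f = 0.9: 98.6%

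These shortfalls arise with no patient missing or reducing a dose.

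**Counting reductions.** Protocol 1.2.2 says 150 mg bd was the next reduction level under the original scheme. Protocol 6.8 now has 150 mg bd as the starting level and 125 mg bd as the single reduction. With D set to the patient's own starting dose, a full cycle at 150 mg bd is therefore one reduction and 85.7% for a 175 mg starter, but no reduction and 100% for a 150 mg starter. Both results are correct for the individual, but a single pooled column merges two scales.

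**Where a split could appear.** The SAP's table list produces T 11.3.2.6 (grade 3 or higher AEs), T 11.3.2.12 (AEs leading to discontinuation of AZD6738 or AZD1775), T 11.3.1.2.1 (interruptions and reductions) and T 11.3.1.7 (dose intensity) for each biomarker stratum and for All. None is split by starting dose. The end of the patient listings was not available for this check, so the statement covers the SAP text and the table list before it.

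**Size of the arm.** About 350 − (2 arms × 3 strata × 50) = 50 patients, if the other two arms fill. Both totals are approximate. That is about 17 per stratum, too few to divide by dose within strata.

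**The case against.** The strongest reply is that the SAP follows the protocol. Protocol 8.5.3 has safety summarised by treatment arm, 8.5 pools both starting doses in comparisons, and neither document promises a safety split. The arm is closed in all strata, AZD1775 is no longer supplied, and no decision waits on these tables. They are descriptive, a dosing listing is planned, table shells are still to be drafted, and SAP 4.1.8 allows labelled post-hoc outputs. All of this stands and keeps the point small. It does not make 175 mg bd the right dose, and it does not define D.

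Three stronger readings are tempting, and the documents do not support them.

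- *The outdated dose line causes the pooling.* It does not. Pooling follows from the safety-set rule in SAP 2.1.2, the three-arm layout in 4.1.2 and protocol 8.5.3. Correcting section 1.2.2 alone would split nothing.
- *A split would show whether the dose cut helped.* It would not. The two groups are sequential and non-randomised. Version 5.0 also added Day 8 and Day 15 blood counts, raised the platelet threshold for dosing to 100,000/µL and limited AZD1775 to one reduction. Detection and dose holds may differ for those reasons too.
- *Leaving out the revised-dose PFS analysis departs from the protocol.* SAP 4.2.5, introduced by "The following PFS sensitivity analyses will be considered", lists only ascertainment, evaluation-time and attrition bias. SAP section 6, "CHANGES OF ANALYSIS FROM PROTOCOL", is marked not applicable. But protocol 8.5 makes the revised-dose analysis optional, so its absence is missing detail and the section 6 entry is not shown to be wrong.

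**Conclusion.** The point holds as a correction to the SAP plus an inexpensive improvement in reporting. The dose line in section 1.2.2 is wrong as current text. Because section 3.5.3 does not fix D, a literal reading gives a fully compliant 150 mg starter an RDI of 85.7% instead of 100%. That result depends on D being taken from section 1.2.2. If programmers use each patient's own starting dose, the error does not arise, but the SAP does not tell them to.

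The by-arm safety and dosing tables comply with the protocol; the gap is that they do not show tolerability at the revised dose. A reader might infer that the pooled AE rates materially overstate those at 150 mg bd. The documents give neither the number of patients per starting dose nor AE rates by dose, so no size can be put on that.

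The ceralasertib comparison, alpha, power and the decision to close the arm are unaffected.

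**What to change.** 1. In SAP 1.2.2, list both AZD1775 starting doses for Arm 3: 175 mg bd (original) and 150 mg bd (from protocol version 5.0).
2. In SAP 3.5.3, define D from each patient's assigned starting dose, and state that a dose reduction is counted relative to that dose.
3. For the All population only, keep the pooled Arm 3 column and add descriptive columns by starting dose in T 11.3.2.6, T 11.3.2.12, T 11.3.1.2.1 and T 11.3.1.7. Footnote that the groups are sequential and non-randomised, and that they also differ in the other version 5.0 changes (Day 8/15 blood counts, platelet threshold, one permitted AZD1775 reduction).

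The cost is SAP wording, one starting-dose flag from dosing data already recorded in the eCRF (protocol 7.5), and two extra columns in each of four outputs. Keeping to the All population avoids changing all 16 versions (4 tables × 4 populations). The downside is a few columns with small numbers for a closed arm. No new data, patients or tests are needed.
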